5.7 Withdrawal of Subjects

- **Describe any anticipated circumstances under which subjects will be withdrawn from the research without their consent.**

It is unlikely that participants will be withdrawn from the study without their consent. However, there are circumstances that we would withdraw a participant.

We will withdraw a participant from the study if we identify that their participation is putting their health at risk.

We will withdraw a participant from the study if they miss scheduled study appointment visits without a valid excuse or fail to notifying study team members of their absence. We will provide participants with a warning prior to withdrawal.

We will withdraw a participant from the study if we learn that they were dishonest when answering our screening (inclusion/exclusion) questionnaire.

We will withdraw a participant from the study if they arrive for study procedures while under the influence of illegal drugs or alcohol.

- **Describe the consequences of a subject's decision to withdraw from the research and the procedures for orderly termination of participation by the subject (e.g., the subject contacting the investigator for an end-of-study visit).**

Participation in this study is voluntary. All participants have the option to choose not to participate in the study or to withdraw from the study at any time without penalty, consequences or loss of VA or other benefits.

- **Describe procedures if a subject is withdrawn or withdraws from the intervention portion of the study but agrees to continue in the follow-up phases or for safety outcome purposes.**

We will not perform follow-up testing with any participant that withdraws or is withdrawn from the study.

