Participants will be stratified by gait speed (half of the participants will have a preferred over ground gait speed ≥ 0.5 m/s and half of participants will have a preferred over ground gait speed < 0.5 m/s) and then randomized into two locomotor intervention groups:

The **Control group** will receive high intensity locomotor training performed on a treadmill [60].

The **Experimental group** will receive high intensity locomotor training performed on a treadmill in a movement amplification environment created by the Agility Trainer.

We will conduct **clinical outcome measures** to assess changes in functional gait and balance and quality of life. We will conduct quantitative **laboratory assessments** to evaluate changes in dynamic balance and associated gait patterns. Finally, to assess if the effects of locomotor training impact participation in walking activities outside of the laboratory/clinical setting, we will measure daily **steps taken in the home and community**.

To ensure that gait and balance are stable prior to beginning the intervention, we

will measure 10 m walk speed and Berg Balance Scale score during an initial **Screen**. These two measures will be repeated a week later during the Baseline (**BSL**) assessment session to ensure the participant's initial performance is stable. If measures are not stable, measures will be repeated a week later. If measures do not stabilize after three-weeks of testing, the participant will not be enrolled in the training intervention. Clinical outcome measures and laboratory assessments will be performed at four time points (**BSL**, **Mid**, **Post**, and **Follow Up**) encompassing the 20-session training intervention (Figure 7). Average number of steps taken in the home and community environment will be estimated from data recorded during 1-week periods occurring at three time points corresponding with **BSL**, **Post**, and at the 3-month **Follow Up**. (Figure 7).

Figure 7. Timeline of the 22 to 26 week schedule for assessments and locomotor training intervention. The length of each individual study segment is indicated.

Daily Steps Assessment	Training Intervention	Training Intervention	Daily Steps Assessment	Daily Steps Assessment
Screen 1-Day	Stepping 1-week	BSL 1-Day	Sessions 1-10 3-5 Weeks	Mid 1-Day
Screen, Consent, 10 MWT, BBS	Clinical And Laboratory Assessments		Clinical And Laboratory Assessments	Clinical And Laboratory Assessments

Locomotor Training Interventions

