We recognize that there is an interaction between the two decision-making trees. Specifically, increasing balance-challenges may increase the cardiovascular demands of walking, and increasing walking speed may increase the challenge to maintain dynamic balance. Based on our goal to provide targeted dynamic balance training, we will prioritize successful accomplishment of the task and stress progression of the dynamic balance demands (elimination of any handheld assist, progression of movement amplification gains, and progression of the balance-challenging tasks). We realize that for lower functioning participants prioritizing the balance challenging components of walking may result in HR and RPE below the target threshold. However, our pilot testing found that we were able to consistently adjust the movement

amplification gains, balance-challenging tasks, and walking speeds in a manner that consistently placed individuals in the target HR and RPE zone.

Documentation of Intervention

A research assistant will be present at every session to assist the physical therapist and document the following events at every training session. Specifically, we will record:

Vital signs before, during, and after training;

Total time walking within the 60-minute session;

Total number of steps (StepWatch, Modus, Washington DC);

Walking speeds:

Number of times **physical assistance** (from the physical therapist or overhead safety support) was provided to prevent fall (fall defined as inability to recover loss of balance without physical assistance);

Specific balance-challenging tasks practiced each session;

Movement Amplification environment gains (if applicable); and

Exertion and workload - monitored via heart rate and the 6-20 RPE scale throughout the session.

Assessment of Locomotor Training Effects

Clinical Outcome Measures

We will collect clinical outcome measures at four time points (BSL, Mid, Post, and Follow Up) surrounding the training intervention. Study personnel performing the clinical assessments will be blinded to the intervention. We will first collect demographic information and a brief medical history including:

- Demographic variables: age, gender, date of birth (BSL only)
- Date of spinal cord injury, level of injury, and cause of injury (BSL only)
- Current and past medical history (BSL only)
- Current medications
- Current ambulatory ability in the home and community including any assistive devices used during ambulation

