Fourth, study information will be posted on <http://www.clinicaltrials.gov>. Interested individuals will be directed to contact the study PI and research staff by phone or mail.

Finally, a recruitment will be posted on the PI's laboratory website. Interested individuals will be directed to contact the study PI and research staff by phone or mail.

- **Describe any payments to subjects, including the amount, timing (at the end of the study or pro-rated for partial study participation), method (e.g., cash, check, gift card), and whether subjects will experience a delay in receiving the payment.**

All participants will receive a stipend of \$25 for visits including laboratory assessments and clinical outcome measures or \$20 for visits that include participation in the locomotor training intervention. Participants will also receive vouchers for parking.

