5.6 Data Analysis

- Provide sample size determination and analysis (include anticipated rate of screen failures, study discontinuations, lost to follow-up etc.).**

Our primary measure to assess dynamic balance during walking is the Lane Width Optimization Test. The test challenges participants to maintain their medio-lateral COM position within a target lane during treadmill walking. If successful, the difficulty of the task becomes progressively more difficult by continually narrowing the width of the target lane until the participant is unable to maintain the target position. The lateral COM excursion per stride during the narrowest lane width achieved **provides a quantitative measure of dynamic balance during gait**. A reduction in the minimum lateral COM excursion following training would indicate improved dynamic balance during gait.

We performed a power analysis to determine the minimum sample size required to detect significant changes in dynamic balance using the lane width optimization test. To estimate the population variability, we used data from 13 individuals with iSCI, having similar characteristics to the target population, performing unassisted treadmill walking [102]. We found that typical lateral COM excursion per stride during preferred speed treadmill walking was 0.083 ± 0.014 m (mean \pm standard deviation). To estimate effect size, we used pre- and post-intervention data from three individuals with iSCI who received 16-18 high intensity locomotor training sessions performed in the movement amplification environment. Following the intervention, these individuals improved dynamic balance (decreased their lateral COM motion excursion during walking) by 32-36%. To detect a 20% difference in improvements in dynamic balance between training groups we will need a sample size of 7 individuals per group at $\alpha = 0.05$ and a power of 80%. We plan to enroll 46 individuals. A recent locomotor training intervention using individuals with iSCI, conducted by one of our study team members at a nearby facility, lost 12% of their participants to drop out [60]. With a conservative estimate that we will lose 20% of participants to drop out, an initial enrollment of 46 individuals would yield 14 high functioning and 14 low functioning participants (stratified based on the gait speed). This number, double that estimated by the power analysis, should be sufficient to assess training effects on dynamic balance.

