Specific Aim 1: To test if our primary measure, changes in dynamic balance during walking, is different between the two groups following the two interventions, we will compare changes in participants' COM lateral excursion during the lane width optimization test across the four assessment periods (BSL, Mid, Post, Follow Up) and between intervention groups (Control and Experimental). To account for the correlation that arises from measuring multiple data points within each participant over time (i.e. data measured from the mid- assessment period from a specific participant will bear more resemblance to data measured from the BSL- assessment period from the same participant than a different participant) we propose to model the primary outcome using a linear mixed effects model. We will use an indicator variable for the group assignment, i.e. 1=Experimental, 0=Control, to test for the effect of intervention while controlling for potential confounders such as initial walking speed, severity and location of the SCI, spasticity, and age. The strength of the linear mixed effects models is that it can accommodate multiple data points from a single participant and can also handle missing data when data is missing at random. We will apply a similar strategy for fitting a secondary analysis to examine changes in preferred walking characteristics (average and variability of step width, step length, and minimum lateral MOS) and outcome measures (10 MWT, FGA, ABC etc.) across the four assessment periods and between intervention groups. We will transform the variables, such as log-transformation, as needed to meet the model assumption of normality.

Specific Aim 2: To test if our primary measure, changes in steps per day, are different following the two interventions, we will compare changes in participants' average steps per day across the three assessment periods (BSL, Post, Follow Up) and between intervention groups (Control and Experimental). Similar to the methods proposed above, we will model the primary outcome using a linear mixed effects model. We will use an indicator variable for the group assignment, i.e. 1=intervention, 0=control, to test for the effect of intervention while again controlling for potential confounders such as initial walking speed, severity and location of spinal cord injury, spasticity, and age.

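### The plan has no assessment route for participants who stop training but are willing to be tested, and its missing-at-random models have no sensitivity analysis

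*Combined protocol and SAP*

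**What the plan says.** Section 5.7 (Withdrawal of Subjects) carries a template prompt about a person who is withdrawn or "withdraws from the intervention portion of the study but agrees to continue in the follow-up phases". The only reply is "We will not perform follow-up testing with any participant that withdraws or is withdrawn from the study". The same section lists when the team withdraws someone from the study: risk to health, unexcused missed visits, dishonest screening answers, and attending under the influence of drugs or alcohol.

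Section 5.6 (Data Analysis) fits a linear mixed effects model for Aim 1, partly because it "can also handle missing data when data is missing at random". Aim 2 uses a similar model. Both adjust for initial walking speed, injury severity and location, spasticity and age. The sample size text allows for attrition: "With a conservative estimate that we will lose 20% of participants to drop out". It also cites 12% in an earlier trial.

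Section 5.1 places the laboratory and clinical assessments at baseline, Mid, Post and Follow Up. Daily steps "will be estimated from data recorded during 1-week periods occurring at three time points corresponding with" baseline, Post and the 3-month Follow Up, so there is no Mid step count. At each session a research assistant is there to "assist the physical therapist and document the following events at every training session". Those records are not named in the analysis model.

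I found no missing-data sensitivity analysis in the document as supplied. Some pages were removed before review, but sections 5.6 and 5.7, where one would normally sit, are present.

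**The concern.** A comparison of all randomised participants needs outcomes from people who stop training as well as from those who finish. Not testing someone who has withdrawn consent is proper, and nothing here questions it. At issue are people who stop training and would still attend assessments. The prompt asks about them, and the reply offers them nothing.

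The two aims are not equally exposed. For Aim 1, a person who leaves after Mid still contributes baseline and Mid values. For Aim 2, anyone who leaves during training contributes baseline steps only, so all information on change comes from those who reach Post. Falls since the previous assessment are also collected at assessments and would be lost.

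Reasons for leaving could differ by arm. Section 5.1 lists pelvic-harness discomfort as a risk, the Introduction describes the harness as part of the Agility Trainer, and only the Experimental group trains with that device. Without a sensitivity analysis, a reader cannot judge how far either result depends on the missing-at-random assumption.

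**Working it through.** **Inputs from section 5.6.** Enrolment 46; planned loss 20% (12% in the cited trial); lateral excursion 0.083 m, SD 0.014 m; target difference 20%.

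**Assumptions.** Equal arms. The 20% is read as a share of the baseline mean: 0.20 × 83 mm = 16.6 mm. The SD comes from preferred-speed walking, not the Lane Width test, and is used for want of a better figure.

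**1. Number lost.** 46 × 0.20 = 9.2, leaving 36.8, or 18.4 per arm. At 12%: 46 × 0.12 = 5.5, leaving about 20.2 per arm. The plan's own retained figure, 14 + 14 = 28, does not reproduce: 1 − 28/46 = 39% loss. That is a separate matter; I use the stated 20%, which is the milder case.

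**2. Bias in Aim 1 if missing at random fails.** Simulation with 1,000,000 per arm. Baseline, Mid and Post each have SD 14 mm and a common correlation r of 0.5, 0.7 or 0.8. Post gains are 33% and 13% (a 20-point gap), half reached by Mid. Dropout before Post is logistic, with log-odds +1 per SD of worse Post excursion in one arm, and random in the other. Within each arm, Post is regressed on baseline and Mid among those observed, then predicted for everyone. Every setting here is assumed; the listed covariates and Follow Up are not modelled. A positive sign means the Experimental advantage is overstated.

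| Loss per arm | r | Outcome-dependent in Experimental | Outcome-dependent in Control |
|---|---|---|---|
| 20% | 0.5 | +1.7 mm | −1.7 mm |
| 20% | 0.7 | +1.1 mm | −1.1 mm |
| 20% | 0.8 | +0.8 mm | −0.8 mm |
| 12% | 0.5 | +1.0 mm | −1.0 mm |
| 12% | 0.7 | +0.7 mm | −0.7 mm |
| 12% | 0.8 | +0.5 mm | −0.5 mm |

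The bias is about zero if the mechanism is the same in both arms, or if dropout follows the observed Mid value. Halving the log-odds at 20% loss gives 0.4 to 0.9 mm.

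**3. Against precision.** SE = 14 × √(1 − r²) × √(2/18.4) = 4.00, 3.30 and 2.77 mm for r = 0.5, 0.7 and 0.8. Bias/SE = 1.68/4.00 = 0.42, 1.11/3.30 = 0.34 and 0.75/2.77 = 0.27. As a share of the target, 1.68/16.6 = 10% and 0.75/16.6 = 5%.

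**4. What retention could recover.** These figures cover all dropouts, not only willing ones. Recovering a random half removes about 0.4 to 0.9 mm of the bias. Full recovery multiplies the SE by √(18.4/23) = 0.894 (11% smaller); half, by √(18.4/20.7) = 0.943 (6% smaller).

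**5. Is return to baseline enough on its own?** With equal 20% loss it takes 16.6 mm to 16.6 × 0.80 = 13.3 mm. With 10% Experimental and 30% Control loss it gives (0.33 × 0.9 − 0.13 × 0.7) × 83 = 17.1 mm, above the target. Reversed, it gives (0.33 × 0.7 − 0.13 × 0.9) × 83 = 9.5 mm. It is therefore not reliably conservative, and the arms must be varied separately.

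**Aim 2.** No SD for steps per day is stated, so no size can be computed.

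**The case against.** The strongest objection is textual. The sentence bars testing of people who leave the study, and nowhere does the plan say that stopping training is leaving the study. That is right, and the reading rests on the prompt being answered. Even on the narrow reading, though, the people the prompt asks about are left without a procedure.

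Second, the model is not naive. It conditions on earlier values and a useful covariate list, keeps partial data, and uses group assignment with no per-protocol restriction. Harness discomfort is mitigated by padding and gradual force increases. All of this stands and makes missing at random more plausible, but it does not test the assumption.

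Third, several team-initiated withdrawals are unlikely to leave someone both willing and testable, particularly as the laboratory test is treadmill walking without assistive devices. This also stands, so recovery will be partial.

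A reader might infer that outcomes missing by rule make the analysis invalid, or that the rule favours the Experimental arm. The documents support neither. A rule that stops data collection does not show that missing at random fails, and the same mechanism placed in Control gives the mirror-image bias.

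**Conclusion.** The point holds as a correctable weakness, not a fatal flaw. The plan gives no route for assessing willing participants who stop training, and it relies on missing at random, given covariates and earlier values, without testing that reliance.

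For Aim 1 the expected effect is modest and of unknown direction: about 0.8 to 1.7 mm either way at 20% loss in the one-arm scenario, at most about 0.42 SE, and only the willing share of it can be recovered. An effect as large as the target would survive; the check matters more if the true effect is smaller. Aim 2 is structurally more exposed, but its size cannot be stated.

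This rests on reading section 5.7 through its prompt, and on the assumed correlations, gains and dropout model.

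**What to change.** In section 5.7, leave the withdrawal criteria as they are, but distinguish stopping training from withdrawing consent to assessment. Invite everyone who stops training to whichever of Mid, Post and Follow Up remain, with step monitoring and falls reports, unless they decline or testing is unsafe. Mid and Post are otherwise set by session count and have no date for someone who stops early, so fix calendar dates from randomisation that match the planned schedule. Record the reason and date of stopping by arm.

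In section 5.6, state that all randomised participants stay in the model by assigned arm. For both aims, prespecify a sensitivity analysis in which the departure from missing at random varies separately by arm (delta adjustment or tipping point), with return to baseline as one scenario.

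**Cost.** Protocol and consent wording, plus at most 9 × 3 = 27 visits at 20% loss, all within the 46 × 4 = 184 that full retention would need. The plan pays $25 "for visits including laboratory assessments and clinical outcome measures", so stipends are at most 27 × $25 = $675, or 9 × 2 × $25 = $450 if everyone leaves after Mid. Staff, parking and laboratory time are extra and not priced in the plan. Some people will decline or be out of contact.

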6.0 Reporting

- **Include procedures for reporting unanticipated problems, serious adverse events, and protocol deviations.**

Any unanticipated deaths will be reported to both the Hines IRB and the Northwestern University IRB within 24 hours of becoming aware of them. Any serious adverse events will be reported to the Hines IRB and Northwestern IRB within 48 hours of becoming aware of the event. All unanticipated adverse events or unanticipated problems involving risks to research participants or study personal will be reported to the Hines IRB and Northwestern University IRB within 48 hours. Any adverse event directly or indirectly related to the study, such as loss of confidentiality or emotional trauma, will also be reported to the Hines IRB and the Northwestern University IRB. Privacy and Data security breaches will be reported to the Hines ISO and Northwestern University ISO immediately.

- **Include information about whether the study has a Data Monitoring Committee and if so, how often it will meet.**

[name] and [name] will jointly be responsible for carrying out the Data Safety Monitoring Plan. The decision to have [name] monitor safety of the trial was based on the simplicity and limited size of the proposed project. Specifically, the following factors were considered - the proposed study is low risk, [name] are not blinded to the study interventions, the study involves less than 40 total participants, and experimental testing and training sessions will be conducted at a single location.

7.0 Privacy and Confidentiality

- **Describe whether the study will use or disclose subjects' Protected Health Information (PHI).**

The study will collect PHI from study participants.

- **Describe the steps that will be taken to secure the data (e.g., training, authorization of access, password protection, encryption, physical controls, Certificates of Confidentiality, and separation of identifiers and data)**

All participants will be given a secret identification code. All experimental data collected from participants will be identified only with this identification code. Data that link the participant to the identification code will be kept in a locked file cabinet.

All hard data recorded from this study will be stored in a locked file cabinet. All electronic data from this study will be coded. A complete copy of all original data will be stored in secure folders on both the Hines VA and Northwestern University servers. Only approved study-team members will be given access to data stored on the servers.

Participants' responses to questionnaires, and medical history questions and clinical testing will be recorded by hand by authorized study personnel. These forms will be identified strictly by the participant's secret identification code. This data will be entered into Microsoft Excel Spreadsheets run on an encrypted VA computer by authorized study personnel. This data too will only be identified using the participant's identification code. When not in use by authorized study personnel, all hardcopies of these forms will be locked in a secure file cabinet in the PI's office located at:

[name].

The file cabinet will be accessible by the PI and approved study personnel. If authorized personnel leave the research team, their access to data will be terminated.

Electronic data collected from motion analysis cameras, load cells, step monitors, heart rate monitors, and other analogue devices will be de-identified. This data will be labeled with the participant's secret identification code. The data will be stored on hard drives and processed in Visual 3-D, MATLAB, and LabVIEW on secure encrypted computers located at:

[name].

Audio recordings from the interview to understand participants' perception will also be de-identified and stored on secured computers at the above location. The electronic data will be accessible only by the PI and approved study personnel.

Data will be stored for 6 years after completion of the study. Only the PI and sub-investigators will have access to the data during this time. The study team members who collect hard copy data during the experiment will be responsible for receipt and transmission of the data from the laboratory to a locked filing cabinet. A digital copy of all original data collected for the project will be transferred to a secure Hines VA server. A VA-approved encrypted flash drive issued to an authorized member of the study team will be used to transfer data from the Northwestern server to a secure study folder on the Hines VA server. Only an authorized study team member

will have access to the encrypted flash drive and study data. The authorized member of the study team will maintain possession of the flash drive at all times. Once the data are transferred, the data on the flash drive will be erased.

If unauthorized use, disclosure, transmission, removal, theft, loss or destruction of VA research-related protected health information (PHI) should occur, in accordance with VA Policy, within one hour of becoming aware of the unauthorized use, disclosure, transmission, removal, theft, loss or destruction of VA research-related PHI, a member of the research team will report the incident to the ACOS for Research, the facility ISO, and the facility PO.

- **If data and biological specimens will be banked, specify.**

Data and biological specimens will not be banked.

